6.2 Justification for Study Design, Dose, and Endpoints

This study was designed based on the requirements of the China Food and Drug Administration (CFDA) for successful registration of dexlansoprazole in China. Phase 3 safety and efficacy trials with dexlansoprazole will be performed concurrently in China. A single-dose study will provide adequate information on the PK of dexlansoprazole in Chinese subjects to allow the data to be bridged to data previously acquired in North American and Japanese populations at both the 30 and 60 mg doses.

This is a single-center, open-label, single-dose, 2-arm parallel study using dexlansoprazole delayed-release capsules (30 and 60 mg). Healthy adult Chinese subjects will be enrolled. Since PPIs are intended to be used by both genders, effort will be made to enroll an equal number of men and women. The study will assess the PK of dexlansoprazole 30 and 60 mg delayed-release capsules.

The CYP2C19 PM phenotype is present in 12% to 23% of the Asian population, and the prevalence of CYP2C19 PMs in Chinese subjects is similar to that of other Asian populations [3].

The CYP2C19 isozyme is a polymorphic enzyme that is involved in the metabolism of dexlansoprazole, and administration of dexlansoprazole may result in higher plasma levels in subjects who are CYP2C19 PMs [1]. Therefore, the CYP2C19 metabolizer status of the subjects will be determined and, if appropriate, the effect of metabolizer status on the PK of dexlansoprazole will be assessed.

The objective of the study is to evaluate the PK of dexlansoprazole at both doses that will be included in the phase 3 studies. Standard PK parameters will be calculated. The design of the study will provide information on the PK of a single dose of dexlansoprazole 30 and 60 mg in healthy Chinese subjects. The safety of dexlansoprazole delayed-release capsules has been evaluated following oral administration in phases 1 and 3 studies. In the previous phase 3 studies, dexlansoprazole 30 and 60 mg had a comparable safety profile to lansoprazole 30 mg. Dexlansoprazole delayed-release capsule doses of 30 and 60 mg were well tolerated.

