13.1.3 Pharmacokinetic Analysis

The concentration of dexlansoprazole in plasma will be summarized by scheduled sampling time points and dose group using descriptive statistics. Individual plasma concentration data will be presented in a data listing.

Descriptive statistics (number of subjects, arithmetic mean, SD, %CV, median, minimum and maximum) will be used to summarize the plasma PK parameters for dexlansoprazole from each dose group.

A more detailed analysis will be presented in the SAP.

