7.10 Pharmacokinetic Analysis

All PK summaries will be based on the PK set. PK parameters of dexlansoprazole will be derived using non-compartmental analysis methods. They will be determined from the concentration-time data for all evaluable subjects. Actual sampling times, rather than scheduled sampling times, will be used in all computations involving sampling times.

Serial blood samples for determination of dexlansoprazole concentrations will be collected on Day 1 (within 30 minutes before dosing) and at 0.5, 1, 1.5, 2, 3, 4, 5, 6, 7, 8, 10, 12, 16, and 24 hours post dose. The concentration of dexlansoprazole in plasma will be summarized by scheduled sampling time points and dose group using descriptive statistics. Individual plasma concentration data will be presented in a data listing. Subject phenotypes will be listed with the concentrations.

The PK parameters of dexlansoprazole will be determined below from the concentration-time profiles for all evaluable subjects. Actual sampling times, rather than scheduled sampling times, will be used in all computations involving sampling times. The following PK parameters will be calculated:

Symbol/Term	Definition
Plasma	
AUC _{last}	Area under the plasma concentration-time curve from time 0 to time of the last quantifiable concentration.
AUC _∞	Area under the plasma concentration-time curve from time 0 to infinity.
C _{max}	Maximum observed concentration.
CL/F	Apparent clearance after extravascular administration.
λ _z	Terminal disposition phase rate constant.
t _{1/2z}	Terminal disposition phase half-life.
t _{max}	Time of first occurrence of C _{max} .
V _z /F	Apparent volume of distribution during the terminal disposition phase after extravascular administration.

Descriptive statistics (number of subjects, arithmetic mean, SD, %CV, median, minimum and maximum) by dose groups will be provided for dexlansoprazole plasma PK parameters. Geometric means will be calculated for Cmax and AUCs. Individual plasma PK parameters will be presented in a data listing. Subject phenotypes will be listed with the PK parameters.

No inferential statistical analysis will be performed. Additional summaries by phenotypes may be performed if there are sufficient number of subjects for each phenotype. More information please refer to separate clinical pharmacology analysis plan (CPAP).

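### Does it matter that the SAP gives geometric means for Cmax and the AUCs but plans no geometric CV or confidence interval?

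*SAP*

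**What the plan says.** Protocol 13.1.3 sets the basic summary by dose group: "Descriptive statistics (number of subjects, arithmetic mean, SD, %CV, median, minimum and maximum) will be used to summarize the plasma PK parameters". It then hands over the detail: "A more detailed analysis will be presented in the SAP".

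SAP 7.10 repeats that list and adds one item: "Geometric means will be calculated for Cmax and AUCs". It also provides that "Individual plasma PK parameters will be presented in a data listing", with each subject's phenotype shown beside the values. On testing it says "No inferential statistical analysis will be performed". On metabolizer status it says "Additional summaries by phenotypes may be performed if there are sufficient number of subjects for each phenotype". The section ends by referring the reader to a separate clinical pharmacology analysis plan, which is not among the documents supplied.

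On purpose, Protocol 6.2 says that a single-dose study "will provide adequate information on the PK of dexlansoprazole in Chinese subjects to allow the data to be bridged" to North American and Japanese data. Protocol 13.3 and SAP 6.0 state that there was no formal sample size calculation, and the Protocol 2.0 summary states that the study is not powered.

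**The concern.** The SAP chooses a log-scale centre for its primary endpoints but reports spread only on the arithmetic scale: the %CV stands in the list with the arithmetic mean and SD. Neither document names confidence intervals, but the ordinary reading of an unqualified no-inference sentence is that there will be none. A geometric CV is not excluded; it is simply not listed.

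In a study that exists to estimate exposure, has no sample size calculation and is meant to feed a bridging argument, the interval around each geometric mean is the natural statement of what 20 subjects per group deliver. If it could not be obtained from the planned output, readers would have a point estimate of the primary endpoints without a usable measure of its precision. Because the geometric mean appears in the SAP and not in the protocol, the two documents may also seem to disagree.

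**Working it through.** **Do the documents conflict?** No. Protocol 13.1.3 leaves the more detailed analysis to the SAP, so the geometric mean is an authorised addition. The protocol's list is also not purely arithmetic, since it includes the median, minimum and maximum.

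**Is there a figure to reproduce?** Only 20 + 20 = 40, which agrees. The documents give no alpha, power, effect size, SD or CV.

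**Is information lost?** Not from the listings. With each subject's Cmax, AUClast and AUC∞ available, the log-scale mean, SD, geometric CV and t interval follow exactly, overall or by phenotype.

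**Would a reader with only the summary table be misled?** This can be checked for AUC.

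Inputs:
- n = 20 per group (SAP 6.0).
- Share of poor metabolizers (PMs) p = 0.12 to 0.23 (Protocol 6.2).
- AUC ratio of PMs to extensive metabolizers of 4, the inverse of the CL/F ratio in Protocol 4.1. It comes from multiple dosing in Japanese men.
- Within-phenotype log-SD s = 0.3 to 0.6. This is an assumption; the documents give no value.

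Formulas: total log-SD = √(s² + p(1−p)(ln 4)²), with (ln 4)² = 1.922. The 95% factor = exp(2.093 × log-SD / √20).

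| p, s | Variance | Log-SD | 95% factor | Interval |
|---|---|---|---|---|
| 0.12, 0.3 | 0.090 + 0.203 = 0.293 | 0.541 | 1.288 | −22.4% to +28.8% |
| 0.23, 0.3 | 0.090 + 0.340 = 0.430 | 0.656 | 1.359 | −26.4% to +35.9% |
| 0.12, 0.6 | 0.360 + 0.203 = 0.563 | 0.750 | 1.421 | −29.6% to +42.1% |
| 0.23, 0.6 | 0.360 + 0.340 = 0.700 | 0.837 | 1.479 | −32.4% to +47.9% |

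The log-SD can be recovered from statistics the SAP does plan, in two ways:
- From the two means: log-SD = √(2 ln(arithmetic mean / geometric mean)).
- From the %CV: log-SD = √(ln(1 + CV²)).

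Both relations are exact for a lognormal variable and approximate for this two-phenotype mixture, so they were tested by simulation, with 100,000 groups of 20 per setting. Coverage of the true geometric mean by the nominal 95% interval:

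| p, s | Log-scale interval | Rebuilt from the two means | Rebuilt from %CV |
|---|---|---|---|
| 0.12, 0.3 | 92.4% | 92.8% | 93.6% |
| 0.23, 0.3 | 93.8% | 94.5% | 95.4% |
| 0.12, 0.6 | 94.8% | 94.6% | 94.3% |
| 0.23, 0.6 | 94.7% | 94.5% | 93.6% |

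The log-SD recovered from the two means has a median 0–7% above the directly computed one, so the rebuilt interval is close in width as well as in coverage.

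**What of the poor coverage of an arithmetic interval?** In the same settings, the arithmetic mean ± t × SD/√20 covers the true arithmetic mean only 86–91% of the time. That concerns a different quantity. It does not show that the geometric mean's precision is unrecoverable, because it ignores the geometric mean the SAP already plans.

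**The case for a change.** The best case for the extra columns has three parts.

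First, the reported %CV cannot simply be attached to the geometric mean. With within-phenotype CVs of 30–50%, the mixture gives an arithmetic CV of 81–97% but a geometric CV of 58–87%. This stands as a caution to the reader. It is not a loss, because the conversions above and the listings both give the log-scale spread.

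Second, an interval computed afterwards is not prespecified. That is true, but prespecification guards against choosing among analyses after seeing the data. Here the log-scale t interval is a standard computation on listed values, and no conclusion in either document turns on where it falls.

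Third, the bridging aim calls for a statement of precision. But neither document plans a bridging comparison within this study, and a pooled interval for one dose group is not that comparison. It also partly reflects the phenotype mix: expected PMs per group are 20 × 0.12 = 2.4 to 20 × 0.23 = 4.6, and each additional PM multiplies the group's geometric mean AUC by 4^(1/20) = 1.072. The SAP already supplies what is needed to read that, by listing phenotype with the PK parameters, summarising genotype and phenotype (SAP 7.12) and allowing phenotype summaries where numbers permit.

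The separate clinical pharmacology analysis plan may also specify these statistics. Absence from the SAP therefore does not establish absence from the full plan, though the conclusion here does not depend on it.

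**Conclusion.** The concern does not hold. It is true that no geometric CV or interval is listed, but following the plan as written gives sound descriptive results. No stated figure or rule is wrong, and the protocol and SAP agree. Both statistics can be computed exactly from the listed individual values for all three primary endpoints. For AUC, even the summary table supports an interval with 92.8–95.4% coverage, against 92.4–94.8% for the directly computed one.

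The coverage figures rest on the assumed within-phenotype log-SD of 0.3 to 0.6, a two-phenotype lognormal model, the protocol's 12–23% PM range and its 4-fold clearance ratio. No such figures are given for Cmax, since the documents supply no phenotype ratio for it. The argument from the listings needs none of these assumptions and covers Cmax too. Adding two columns to the table would be a convenience for the reader and would change no result.

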Dexlansoprazole is primarily metabolized by the cytochrome P450 (CYP) enzymes CYP3A4 and polymorphic CYP2C19 [1]. The CYP2C19 poor metabolizer (PM) phenotype is present in 12% to 23% of the Asian population, and the prevalence of CYP2C19 PMs in Chinese subjects is similar to that of other Asian populations [3]. Study TAK-390MR/CPH-002 assessed the PK of multiple doses of dexlansoprazole 30 and 60 mg capsule doses in male Japanese PM and extensive metabolizer (EM) subjects. In the Japanese PMs, dexlansoprazole $t_{1/2z}$ was approximately 3 times longer than in EMs, and apparent clearance after extravascular administration (CL/F) in the EMs was approximately 4-times greater than PMs. Although the availability of PK data in PMs in the Caucasian and African American population is limited, it is expected that dexlansoprazole exposure in these races will be affected by CYP2C19 phenotypes as well.

The majority of the dexlansoprazole capsule phase 1 studies were conducted in the United States. As development of dexlansoprazole expands to other countries, additional studies are needed to bridge between the data acquired previously in North American and Asian populations.

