9.1.12 Sample Collection for Genotype Analysis

Genotyping and phenotyping analysis for CYP2C19 will be required for all subjects because dexlansoprazole is metabolized by the polymorphic isozyme CYP2C19. On Day 1, one blood sample (approximately 2 mL) for genotype analysis will be collected into vacutainers containing anticoagulant K₂EDTA according to the schedule in [Appendix A](#). Instructions for sample processing and shipment are provided in [Appendix E](#).

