7.9 Study Drug Exposure and Overdose

Study drug administration and overdose information will be listed. Standard meal information will also be presented. Summaries of PK data will be provided by dose group. No other summary statistics for the extent of exposure to study drug or compliance calculations will be performed for this study.

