7.12 Genotype Analysis

Genotype test will be summarized by Genotype and phenotype, and Blood samples collected for genotype test will be presented in data listing.

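### Should SAP 7.10 fix the PK summaries by CYP2C19 phenotype, rather than leave them optional?

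*SAP*

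**What the plan says.** Protocol 13.1.3 states that descriptive statistics "will be used to summarize the plasma PK parameters for dexlansoprazole from each dose group". SAP 7.9 agrees: "Summaries of PK data will be provided by dose group". SAP 7.10 gives the list: number of subjects, arithmetic mean, SD, %CV, median, minimum and maximum by dose group, with geometric means for Cmax and the AUCs, and no inference.

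Phenotype has a firm place in three passages. Protocol 9.1.12 says "Genotyping and phenotyping analysis for CYP2C19 will be required for all subjects". SAP 7.10 says "Subject phenotypes will be listed with the PK parameters", and makes the same commitment for concentrations. SAP 7.12 says "Genotype test will be summarized by Genotype and phenotype".

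Summaries of PK by phenotype are optional: "Additional summaries by phenotypes may be performed if there are sufficient number of subjects for each phenotype". The next sentence of SAP 7.10 refers the reader to a separate clinical pharmacology analysis plan. Protocol 6.2 is conditional too: metabolizer status will be determined, and its effect on PK assessed only where that is appropriate.

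**The concern.** The protocol treats CYP2C19 status as a main source of variation. Protocol 4.1 says the PM "phenotype is present in 12% to 23% of the Asian population", and reports from a Japanese multiple-dose study that CL/F was about 4 times greater in EMs and the terminal half-life about 3 times longer in PMs. A dose-group mean is then the mean of a mixture and moves with the number of PMs who happen to enrol. Protocol 6.2 names bridging to North American and Japanese data as a purpose, and the Japanese study assessed PMs and EMs.

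Against that background, a summary that may be produced if numbers are sufficient leaves three things open: whether a phenotype table will exist, what counts as sufficient, and whether the two doses would be combined. In an open-label study these could be settled after the PM count and the PK results are known. At stake would be dose-group means that are hard to interpret, and a phenotype comparison chosen after the fact.

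**Working it through.** The plan has no figure to reproduce: both documents say that no formal sample size calculation was made. The check asks how far pooled statistics could move, and whether phenotype cells would be large enough to summarise.

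**Inputs**
- 20 subjects per dose group, 40 in all (SAP 6.0).
- PM prevalence p = 0.12 to 0.23 (Protocol 4.1 and 6.2).
- PM:EM ratio of 4 for AUC, from the CL/F ratio, and 3 for half-life (Protocol 4.1).
- Assumed: these ratios, from Japanese men on multiple doses, carry over to single doses here; every non-PM has EM values; PM counts are independent binomials.

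The documents give no PM:EM ratio for Cmax.

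**PMs per arm.** k ~ Binomial(20, p).
- Expected count: 20 × 0.12 = 2.4 and 20 × 0.23 = 4.6.
- SD of k = √(20p(1−p)): 1.453 and 1.882.

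**Pooled statistics relative to EM, from the PM count alone**

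| Statistic | Formula | Mean, p = 0.12 | Mean, p = 0.23 | SD | CV |
|---|---|---|---|---|---|
| Arithmetic mean AUC | 1 + 3k/20 | 1.36 | 1.69 | 0.218; 0.282 | 16.0%; 16.7% |
| Geometric mean AUC | 4^(k/20) | 1.187 | 1.387 | 0.123; 0.185 | 10.4%; 13.3% |
| Mean half-life | 1 + 2k/20 | 1.24 | 1.46 | 0.145; 0.188 | 11.7%; 12.9% |

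For half-life, SD = (2/20) × 1.453 = 0.145 and (2/20) × 1.882 = 0.188; the CVs are 0.145/1.24 and 0.188/1.46.

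**Median.** With only two values, the median of 20 stays at the EM value for any k up to 9. P(k > 9) is 0.00004 at p = 0.12 and 0.008 at p = 0.23. If within-phenotype CV is assumed to be 30% (not in the documents), the mixture median is 1.05 to 1.12 times EM; at 60% it is 1.10 to 1.23.

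**Imbalance between doses.** PM counts differ by 3 or more between arms with probability 0.22 (p = 0.12) to 0.35 (p = 0.23). As an example, 2 PMs on 30 mg and 5 on 60 mg give an apparent ratio of arithmetic mean AUCs of 2 × 1.75/1.30 = 2.69, where proportionality would give 2.

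**Feasibility of phenotype summaries.** The SAP sets no minimum; 3 per cell is used for illustration.
- One arm, P(k ≥ 3): 1 − 0.563 = 0.437 and 1 − 0.128 = 0.872.
- Both arms: 0.437² = 0.191 and 0.872² = 0.760.
- All 40 subjects, expected PMs 4.8 and 9.2: P(≥ 3) = 0.874 and 0.998.

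So at 12% prevalence a dose-by-phenotype table would lack 3 PMs in at least one arm about four times in five. Combining doses would usually give enough PMs, but it needs dose-normalised values and so rests on dose proportionality, which Protocol 4.1 describes only as apparent and does not report separately for PMs.

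**The case for a change.** The best case for a change is that it is cheap and that the protocol's own figures call for it. Protocol 13.1 leaves the methodology for the study objectives to the SAP, yet SAP 7.10 answers one undefined condition with another. Listings let a reader rebuild a phenotype table, but they do not specify one in advance. A sentence defining sufficiency, a PM count beside each dose-group table and one dose-normalised summary would close the gap without new subjects or samples.

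Part of this stands. The wording is loose, and pooled arithmetic means do depend on the PM count. But the amendment would add little. Phenotype effect is neither an objective nor an endpoint in either document. No test, estimate or decision rule depends on the optional table, so choosing it late offers little to exploit. SAP 7.12 summarises genotype and phenotype, so PM numbers will be visible. Neither document specifies a bridging analysis or says that it would use the pooled tables. A cell minimum of 3 and a dose-normalised pooled table are reasonable preferences, but nothing in the documents requires them, and the second adds an assumption that the present plan avoids. The clinical pharmacology analysis plan may already settle the details.

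**Conclusion.** No change to the plan follows. SAP 7.10 leaves a detail open that analysts can fill sensibly once the PM counts are known, and the open wording agrees with the protocol's own condition. Followed as written, the plan gives a sound description of PK in healthy Chinese subjects at each dose, with median, range, %CV and, for Cmax and the AUCs, geometric means to set beside the arithmetic mean. Phenotype can be read for each subject from the listings, so no information is lost and nothing is biased.

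The mixture effect is real in size: an expected 1.36 to 1.69 times EM for arithmetic mean AUC (CV 16% to 17%), and 1.24 to 1.46 times EM for mean half-life (CV 12% to 13%). It is a feature of the population being described, and a matter for interpretation. These figures rest on carrying the Japanese multiple-dose ratios over to this study, on two phenotype classes only, and on 12% to 23% prevalence. The content of the clinical pharmacology analysis plan is unknown here, so the looseness is shown for SAP 7.10 alone and not for the whole analysis plan.

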13.0 STATISTICAL METHODS

13.1 Statistical and Analytical Plans

A statistical analysis plan (SAP) will be prepared and finalized prior to database lock. This document will provide further details regarding the definition of analysis variables and analysis methodology to address all study objectives.

The targeted review plan will be conducted prior to database lock. This review will assess the accuracy and completeness of the study database, subject evaluability, and appropriateness of the planned statistical methods.

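### Does SAP 7.10's pointer to an undated clinical pharmacology analysis plan leave the primary PK analysis open after database lock?

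*SAP*

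**What the plan says.** Protocol 13.1 states: "A statistical analysis plan (SAP) will be prepared and finalized prior to database lock". On scope it adds: "This document will provide further details regarding the definition of analysis variables and analysis methodology to address all study objectives". Protocol 13.1.3 gives the basic descriptive statistics for PK and ends: "A more detailed analysis will be presented in the SAP".

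SAP 7.10 specifies:
- non-compartmental derivation from actual sampling times;
- eight named parameters, including the three primary endpoints (Cmax, AUClast, AUC∞);
- number of subjects, arithmetic mean, SD, %CV, median, minimum and maximum by dose group;
- for the primary endpoints, "Geometric means will be calculated for Cmax and AUCs";
- listings of individual concentrations and parameters with each subject's phenotype;
- no inferential analysis.

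It then says "Additional summaries by phenotypes may be performed if there are sufficient number of subjects for each phenotype" and closes with "More information please refer to separate clinical pharmacology analysis plan (CPAP". The supplied protocol text does not mention a CPAP. The SAP gives no version or date for it and omits it from its abbreviation and reference lists.

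On metabolizer status, Protocol 6.2 says that "if appropriate, the effect of metabolizer status on the PK of dexlansoprazole will be assessed". SAP 7.12 summarizes the genotype test by genotype and phenotype without any condition.

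**The concern.** The protocol's commitment to finalize before lock covers the SAP, not a document the SAP refers to. PK is the primary objective and the study is open-label. If material PK choices sat only in an undated plan, they could be made once concentrations and genotypes were known.

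The phenotype condition adds to the worry. Protocol 4.1 reports that, in Japanese men, "apparent clearance after extravascular administration (CL/F) in the EMs was approximately 4-times greater than PMs", and puts PM prevalence at 12% to 23%. A summary pooled over phenotypes therefore depends on how many PMs happen to enrol. The SAP guarantees only that pooled summary. Read literally, a shortage of PMs would also withhold the summary of non-PMs, the large majority of each group. Protocol 6.2 wants the data bridged to North American and Japanese results, so the make-up of the pooled figure matters to the reader. The geometric mean also has no log-scale measure of spread beside it.

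**Working it through.** Neither document contains a sample-size or power figure to reproduce; both say no formal calculation was done. The check is a comparison of texts, then arithmetic on the phenotype point.

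**What the SAP leaves open.**

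| Item | Where fixed | Open after lock? |
|---|---|---|
| Parameters, non-compartmental method, actual times | SAP 7.10 | No |
| Summary statistics, including spread | Protocol 13.1.3, SAP 7.10 | No |
| Phenotype beside each individual value | SAP 7.10 | No |
| Genotype and phenotype counts | SAP 7.12 | No |
| PK summary tables by phenotype | SAP 7.10, optional | Yes |
| CPAP version and date | Not stated | Not shown |

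The spread statistics are prespecified, so they cannot be picked after seeing the data. A geometric CV would be an addition to them.

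**How far pooling moves the AUC summary.** Inputs: n = 20 per group (SAP 6.0); PM share p = 0.12 to 0.23 (Protocol 4.1 and 6.2); PM/EM (extensive metabolizer) AUC ratio 4, the inverse of the CL/F ratio in Protocol 4.1, with all non-PMs treated as EMs. The within-phenotype CV is an assumption, 30% to 60%.
- Pooled over non-PM geometric mean: 4^p = 4^0.12 = 1.18; 4^0.23 = 1.38.
- Pooled over non-PM arithmetic mean m: (1 − p) + 4p = 1.36; 1.69.
- Pooled arithmetic CV: √[(1 + CV²)((1 − p) + 16p) − m²]/m. At p = 0.12: 81% (CV 30%) and 103% (CV 60%). At p = 0.23: 84% and 106%.
- Geometric CV: √(exp(v) − 1), with v = ln(1 + CV²) + p(1 − p)(ln 4)². At p = 0.12: 58% and 82%. At p = 0.23: 73% and 95%.

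The documents give no PM/EM ratio for Cmax, so this covers AUC only.

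**How often PMs would be too few.** Take 0 or 1 PM as too few, since no SD exists. The probability is (1 − p)^n + np(1 − p)^(n−1).
- Within one group of 20: 28.9% at p = 0.12; 3.7% at p = 0.23.
- In at least one of two groups: 1 − (1 − 0.289)² = 49%; 1 − (1 − 0.037)² = 7%.
- Over all 40 subjects: 3.9%; 0.04%.

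SAP 7.10 does not say whether the count is per dose group or over the whole study. The answer also depends on the threshold. With illustrative cut-offs, the chance of at least 3 PMs in both groups is 19% to 76%, and of at least 5 in both, 0.7% to 25%.

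**What this shows.** Mixing phenotypes widens and shifts the pooled AUC summary. These figures measure that mixing, not any effect of an undated CPAP. With phenotype printed beside every individual value, each split figure can be computed from the listings.

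**The case for a change.** The strongest case for a change is that the protocol promised one place and one deadline for the detailed PK methods, and the SAP sends the reader elsewhere without a deadline. The remedy would be cheap: a dated reference, a non-PM column and a geometric CV, with no new subjects, visits or samples. Neither document states rules for choosing the points for λz, for acceptable AUC extrapolation, or for concentrations below quantification. These are what a separate pharmacology plan would normally hold, and they enter the primary endpoints.

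Part of this stands. The CPAP's timing is not stated, and the number that counts as sufficient is undefined. But the missing derivation rules are routine conventions of non-compartmental analysis, and Cmax and AUClast do not use λz. The documents do not show the CPAP to be late or incomplete, and it may already contain these rules and the phenotype tables. Protocol 13.1 also provides for a review before lock that covers subject evaluability and whether the planned methods suit the data, a natural point at which to decide on the split.

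The rest does not stand. The optional split matches Protocol 6.2. The literal reading, under which few PMs would suppress the non-PM table, is not the ordinary one: an analyst would summarize whichever phenotype has enough subjects. The extra column and geometric CV are reasonable preferences for a descriptive report, but leaving them out does not make the planned summaries wrong.

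**Conclusion.** No change to the plan is needed. The texts do differ: Protocol 13.1 and 13.1.3 place PK detail in a SAP tied to the lock, and SAP 7.10 adds an undated second document. This is a minor documentation gap. The SAP delivers the core of what was promised, and its pointer offers further information without deferring the primary summary.

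The possible shift from pooling, 1.18 to 1.38 times for the geometric mean AUC, rests on a 4-fold ratio from a multiple-dose study in Japanese men and on treating all non-PMs as EMs. The CV figures also rest on the assumed 30% to 60% within-phenotype CV. Even at the upper end, the shift describes the enrolled mix and can be seen and undone from the phenotype-labelled listings. With no hypothesis test there is no type I error or power to protect, and following the plan as written leads to no wrong result or conclusion. This judgement assumes that the CPAP holds ordinary non-compartmental rules; its content and timing cannot be confirmed from these documents.
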